9.10 Site and Subgroup Heterogeneity

Primary safety and effectiveness endpoints will be reported by site, by gender, and by classification of persistent AF (longstanding vs. non-longstanding). In addition, logistic regression models will be utilized to test for statistically significant differences in the endpoints due to site regions (US and OUS), gender, and classification of persistent AF (longstanding vs. non-longstanding), while also adjusting for age, BMI, baseline comorbid conditions, LVEF, total length of AF, and number of previous catheter ablations. P-values will be reported for each covariate and odds ratios with 95% confidence intervals will be reported for gender and for classification of persistent AF.

This overall goal of this study is to show safety and effectiveness in a representative population of patients with persistent atrial fibrillation and thus it is not powered for separate analysis of individual subpopulations.

10.0 ADVERSE EVENTS

RF ablation using bipolar energy applied epicardially has been used in concomitant procedures for the treatment of AF for over 10 years and the risks are well understood. More recently standalone (or sole therapy) surgical ablation for treatment of atrial fibrillation has been reported by various institutions to be safe, and with varying degrees of effectiveness (depending on the lesion set, procedure, and subject population). Risks and benefits to the subjects are described in the **Clinical Risk/Benefit Analysis (Appendix 4)**. **Adverse Event Definitions** are found in **Appendix 5**.

10.1 Definitions

Adverse Event:

Adverse Event (AE): any undesirable clinical occurrence or change from patient's baseline (or pre-device procedure) condition, whether it is considered device related or not.

Adverse Event Identification: a condition that is one of the following:

- a) A unique symptom or event that is a change from the subject's baseline status
- b) A series of symptoms or events that can be categorized as a single entity based on definitions found herein
- c) A specific diagnosis responsible for a clinical change
- d) A worsening or exacerbation of a pre-existing condition

Serious Adverse Event:

Serious Adverse Event (SAE): any adverse event is considered serious if it results in death, is life threatening, requires hospitalization (initial or prolonged), results in disability or permanent damage, causes congenital anomaly/birth defect, requires intervention to prevent impairment or

damage, or other serious (important medical events) which may jeopardize the subject and may require medical or surgical intervention to prevent one of the above outcomes.

Note: "Death" should not be reported as an adverse event. The cause of death should be reported as an adverse event. The only exception is "Sudden Death" when the cause is unknown.

Unanticipated Adverse Device Effect (UADE):

Any serious adverse effect on health or safety, any life-threatening problem or death caused by, or associated with a device, if that effect, problem, or death was not previously identified in nature, severity, or degree of incidence in the application; or any other unanticipated serious problem associated with a device that relates to the rights, safety, or welfare of subjects [21 CFR part 812.3(s)].

Pre-existing Condition vs. Adverse Event:

A pre-existing condition is defined as a medical condition that is present before treatment (treatment being defined as induction of anesthesia) and is to be reported as part of the subject's medical history. It must be reported as a new AE if the intensity, frequency, or the character of the condition worsens during the study treatment and the AE was determined to have the relationship to the study procedures and/or study devices.

To avoid confusing pre-existing conditions with AEs during data analysis, the study sites must make all attempts to provide start dates for all baseline medical conditions. Any pre-existing condition that now meets the stated criteria as an AE should be recorded on the AE eCRF as an exacerbation of the pre-existing condition and the start date will be recorded as the time when the exacerbation occurred.

10.2 Events Expected to Occur with Epicardial Surgical Ablation Procedure and the Endocardial EP Ablation Procedure

For purposes of this study, the following events are not considered reportable (recorded on eCRF) because they are normally expected to occur in conjunction with treatment for persistent or longstanding persistent atrial fibrillation, atrial fibrillation procedures, or are associated with customary, standard care of patients undergoing minimally invasive cardiac surgery or catheter ablation procedures.

- Chest pain without associated enzyme/ECG changes
- Post-operative pain/post-procedure pain
- Post-anesthesia emesis, nausea, or headache (within 48 hours of procedure)
- Electrolyte imbalance without clinical sequelae following procedure, even if requiring correction
- Low grade temperature increase ($\leq 101^{\circ}\text{F}$ or 38.5°C)
- Dizziness: Imprecise term commonly used to describe various symptoms such as faintness, giddiness, imbalance, lightheadedness, unsteadiness or vertigo
- Elevated White Blood Count, outside the standard laboratory normal value, without signs and symptoms of infection
- Post-Operative/post-procedure hematocrit decrease from baseline measured in the OR, prior to the first incision, not associated with hemodynamic changes, remaining above 25% and requiring < 2 units PRBC's

- Minor, localized tenderness, swelling, induration, oozing, etc. at surgical site or catheter insertion site
- Sinus bradycardia/tachycardia that does not require treatment or intervention
- Systolic or diastolic blood pressure changes that do not require treatment or intervention
- Thrombocytopenia: does not become an AE until treatment is administered
- Atelectasis: collapse of lung tissue affecting part or all of one lung; the alveoli are deflated. This is not considered to be an AE unless treatment other than Chest PT is required or it prolongs hospitalization – Note: this event is expected for surgical procedure only
- Hyperglycemia: The use of insulin in the post op period does not constitute hyperglycemia if during the same hospitalization. An elevated blood sugar of less than 250 mg/dl during the first 48 hours post op does not constitute hyperglycemia
- Pleural effusion unless treatment with thoracentesis or chest tube insertion is required – Note: this event is expected for surgical procedure only
- Pericardial effusion without hemodynamic compromise or treatment
- Atrial Fibrillation / Atrial Flutter / Atrial Tachycardia with or without cardioversion
- Junctional Rhythm requiring temporary pacing

Note: Subjects will undergo general anesthesia and therefore will also be subject to general anesthesia-associated complications and morbidity. These are also not considered reportable (recorded on eCRF) adverse events.

- Pre-planned Surgical Procedures

Any pre-planned surgical procedures at the time of informed consent will not be considered reportable (recorded on eCRF) (whether hospitalization is required or not). Any blood transfusions during preplanned operative procedure are not considered reportable adverse events.

Note: This listing of events is intended to provide guidance to the Investigator / investigational site for the purpose of adverse event reporting. The Investigator should utilize his/her own clinical judgment in evaluating adverse experiences and may decide that the above events should be reported as adverse events.

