10.4 Relationship of Adverse Events

It is the PIs responsibility to assess the relationship of an AE. Adverse events will be assigned an attribution according to the Investigator's best judgement of primary cause. Events will be categorized by relationship to the investigational devices (ASU2, ASU3, ASB2, EMR2, EML2, MAX5, MCR1, MLP1), or the AtriClip (PRO1 or PRO2), procedure [ablation procedure (epicardial or endocardial) or general cardiac surgical procedure, subsequent intervention], concomitant medications, pre-existing condition, intercurrent condition, intercurrent intervention, or unknown.

Device Related Adverse Event: An adverse event, which in the judgment of the Investigator, results from use of the AtriCure Bipolar System, the AtriClip or the endocardial ablation devices.

Procedure Related Adverse Event: An adverse event which, in the judgment of the Investigator, results as a consequence of the procedure (epicardial surgical procedure or endocardial EP procedure or general cardiac surgical procedure, subsequent intervention) and is not specifically related to the use of the AtriCure Bipolar System.

Concomitant Medication-Related Adverse Event: An adverse event is considered to be concomitant medication related when, in the judgment of the Investigator, it is reasonable to believe that the event is associated with concomitant medications used in conjunction with the investigational device and is not otherwise specific to the investigational device (e.g. bleeding associated with anticoagulation medication).

Pre-Existing Condition-Related Adverse Event: An adverse event is considered to be related to a pre-existing condition when, in the judgment of the Investigator, it is reasonable to believe that the event is associated with the subject's pre-existing condition and is not specific to the investigational device, ablation procedure, or general cardiac surgical procedure. Pre-existing conditions that are aggravated or become more severe during or after the procedure should be evaluated on a case-by-case basis to determine if the event may be more appropriately classified as device-, ablation procedure-, or general cardiac surgical procedure-related.

Intercurrent Condition: It is reasonable to believe that the event is directly associated with an intercurrent condition/co-morbidity.

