10.5 Reporting Procedures For Adverse Events

10.5.1 General Reporting Requirements - Non-Serious Adverse Events

The Investigator (or designee) will record **all** AEs (both serious and non-serious and regardless of relationship) in the source documents. AEs will be reported on the eCRF (except those in Section 10.2 as described) from the time of treatment (induction of anesthesia) through Visit 11. Only the AEs listed to be collected (Section 10.5.2) in the annual visits (2–5-year visits) will be reported on the eCRF. Prior to induction of anesthesia, any events will be considered patient medical history. Standard medical terminology should be used when recording AEs. The information as described in 10.3 and 10.4 should be recorded for each AE. The following criteria must also be adhered to by the Investigator:

- Use separate Adverse Event Form to document each series of events.
- The Adverse Event Form must be electronically signed by the Investigator or Co-Investigator (if applicable).
- It is the responsibility of the Investigator to inform their IRB of SAEs as required by their IRB/EC procedures and in conformance with FDA requirements.

Note: It is the responsibility of the Investigator to inform their IRB of non-serious adverse events, as required by their IRB procedures and in conformance with FDA requirements.

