2.1.4 Secondary Safety Endpoints

All secondary safety endpoints are supplemental and intended to provide a more complete picture of the overall safety profile for the DEEP procedure. They will not be tested for labeling purposes.

Statistical Analysis Plan		Page 9 of 22
Sponsor	Study	Version
AtriCure	DEEP Pivotal Study	Version 2.0

1. Major surgical events – This will be a composite safety endpoint within 30 days of the epicardial surgical procedure, as otherwise defined in the primary safety endpoint.
2. Major catheter events – This will be a composite safety endpoint within 7 days of the endocardial catheter procedure, as otherwise defined in the primary safety endpoint.
3. 30-day surgical SAEs – This will include all SAEs that occur within 30 days of the epicardial surgical procedure and that are adjudicated to be related to the device or to the procedure.
4. 12-month DEEP SAEs – This will include all SAEs through the 12-month follow-up visit that are adjudicated to be related to an AtriCure device or to either stage of the DEEP procedure.
5. Unresolved SAEs – This will include all SAEs through the 12-month follow-up visit that are adjudicated to be related to an AtriCure device or to either stage of the DEEP procedure and that are not fully resolved by the 12-months visit. These events shall include any procedure related deaths, strokes with residual disability, unresolved phrenic nerve damage, or other such events that are adjudicated to have resulted in chronic disability or permanent damage.
6. Any serious adverse event through the 12-month follow-up visit, regardless of attribution.
7. Incidence of stroke or TIA at 12-month, 24, 36, 48, 60-month visits.
8. Any esophageal injury that meets all of the following criteria: identified post epicardial ablation, adjudicated by core lab to be a thermal injury with perforation, and related to an AtriCure ablation device, through 30-days post epicardial procedure.

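### Protocol 10.1 ties reporting of a worsened pre-existing condition to a finding of relatedness, against the protocol's own AE and SAE rules, so some SAEs could bypass the CEC and secondary safety endpoint #6

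*Protocol*

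**What the plan says.** Protocol 10.1 contains two rules for a baseline condition that gets worse.

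- The general rule defines an adverse event as an undesirable change from baseline, "whether it is considered device related or not", and lists "A worsening or exacerbation of a pre-existing condition" as one way to identify one.
- The specific rule, under the comparison of pre-existing conditions with adverse events, requires a new AE report if the condition "worsens during the study treatment and the AE was determined to have the relationship to the study procedures and/or study devices". The paragraph that follows carries this to the database: "Any pre-existing condition that now meets the stated criteria as an AE should be recorded on the AE eCRF".

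Elsewhere, 10.4 gives the first causality judgement to the site: "It is the PIs responsibility to assess the relationship of an AE". Section 10.5.1 has all AEs entered in source documents, "both serious and non-serious and regardless of relationship", and puts AEs on the eCRF from induction of anesthesia through Visit 11, apart from the expected events in 10.2. Section 10.5.2 requires all SAEs over the same period with the same single exception. Section 11.1 sends SAEs up to Visit 11 to the CEC.

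In the SAP (2.1.4), secondary safety endpoint #6 is "Any serious adverse event through the 12-month follow-up visit, regardless of attribution".

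**The concern.** For the primary safety endpoint, relatedness is the CEC's decision (Protocol 3.2). The specific rule in 10.1 places an earlier causality judgement, made at the site, in front of that process and lets it decide whether the event is reported. An endpoint meant to ignore attribution would then depend on attribution for one class of events.

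That class is foreseeable. Appendix 4 lists exacerbation of existing congestive heart failure among the possible adverse events, and Protocol 9.3 says heart failure is more frequent in persistent than in paroxysmal AF. An admission for heart failure that the site puts down to underlying disease is the kind of event at stake. In a single-arm study an unreported event simply looks like no event, so any error would make the procedure look safer.

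**Working it through.** No figure in the plan rests on this sentence, so the main check is a comparison of texts.

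**1. What the sentence requires.** It joins two conditions, worsening and a determination of relatedness. It states when a report is mandatory. It does not say in terms that other worsenings are not AEs. But the next paragraph limits eCRF entry to conditions meeting the stated criteria, and the nearest stated criteria are these two.

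**2. The provisions side by side.**

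| Provision (Protocol) | Relatedness condition for a worsened baseline condition? |
|---|---|
| 10.1, AE definition and identification item d | No |
| 10.1, pre-existing condition rule | Yes |
| 10.1, eCRF entry of exacerbations | Yes, by reference to the stated criteria |
| 10.4, class for events related to a pre-existing condition | No; it covers events not specific to device or procedure |
| 10.5.1, AE recording | No |
| 10.5.2, SAE reporting through Visit 11 | No |
| 11.1, SAEs submitted to the CEC | No, but the CEC reviews reported events |

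**3. Whether the general rules settle it.** Section 10.1 defines an SAE as an adverse event that meets a seriousness criterion. The rules in 10.5.2 and 11.1 therefore act on something already classed as an AE. A site that applies the specific sentence stops before reaching them. A site that starts from 10.5.2 reports the event. The protocol does not say which text prevails.

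**4. The time period.** The specific rule also limits the worsening to the study treatment. The same paragraph equates treatment with induction of anesthesia, whereas 10.5.1 collects AEs through Visit 11. Read literally, the two periods differ.

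**5. Endpoints reached.** Endpoint #6 is exposed directly. Endpoints #3 to #5 count events adjudicated as related, so they lose only those the CEC would have called related against the site's view.

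**6. Possible size for endpoint #6 (assumed values only).** Let T be the true proportion of subjects with any SAE, and s the share of those whose only SAE is an unrelated-judged worsening left unreported. Missed subjects = N × T × s; reported rate = T × (1 − s). The documents give neither T nor s. With N = 220, T from 0.30 to 0.50 and s from 0.05 to 0.20:

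- lowest: 220 × 0.30 × 0.05 = 3.3 subjects;
- highest: 220 × 0.50 × 0.20 = 22 subjects;
- a true 40% would be reported as 0.40 × 0.95 = 38% down to 0.40 × 0.80 = 32%.

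**7. Primary safety test, for context.** The plan's N reproduces: [1.960√(0.28 × 0.72) + 0.842√(0.19 × 0.81)]² / 0.09² = 180.8, and with continuity correction 180.8/4 × [1 + √(1 + 2/(180.8 × 0.09))]² = 191.8, so 192. The test is z = (x/n − 0.28)/√(0.28 × 0.72/n), passing below −1.96.

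- n = 192: 41 events give z = −2.05 (pass); 42 give −1.89 (fail). One event is 1/192 = 0.5 percentage points.
- n = 220: 48 events give z = −2.04 (pass); 49 give −1.89 (fail). One event is 1/220 = 0.45 percentage points.

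These limits show where the test turns. They say nothing about how many events the 10.1 sentence would remove.

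**The case against.** The strongest reply is that the protocol, read as a whole, collects these events and that one sentence is badly drafted. Item d of the AE definition includes worsening without qualification. Section 10.4 has an attribution class for events due to a pre-existing condition and adds: "Pre-existing conditions that are aggravated or become more severe during or after the procedure should be evaluated on a case-by-case basis". That class would have little use if unrelated worsening were never an AE. Sections 10.5.2 and 11.1 apply no relatedness filter to SAEs. All of this stands as evidence of intent. It does not remove the conflict, because those rules presuppose an AE and a site may reasonably follow the sentence written for its exact case.

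A reader might go further and infer that SAEs judged unrelated never reach the CEC, that endpoint #6 is undercounted, and that the primary safety result is biased toward success. The documents do not support this.

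- SAEs other than worsened baseline conditions are untouched by the sentence.
- The undercount is conditional on site practice, which the documents do not show.
- To affect the primary endpoint, a worsening would also have to be a listed composite event, within its window, that the CEC would judge related. Heart failure, lung disease and hypertension are not components. A fatal worsening would be, but death is recorded separately as an exit reason (Protocol 4.3).
- The population is restricted. NYHA class IV, ejection fraction below 30%, moderate to severe COPD and refractory hypertension are exclusions (Protocol 4.2.4), and the documents do not say how common milder disease will be.

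**Conclusion.** The contradiction is real and should be corrected. Protocol 10.1 makes a relatedness finding part of the reporting rule for worsened pre-existing conditions, and this conflicts with the AE definition beside it and with 10.4, 10.5.1 and 10.5.2. The consequence is a risk that endpoint #6 is too low and that endpoints #3 to #5 miss events the CEC might have attributed to the procedure or device.

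The importance is moderate. The risk covers one class of event, and its size is unknown; the 3 to 22 subjects above rest wholly on assumed rates and on every such event going unreported. Secondary safety endpoints are exploratory with no inference (SAP 5.6.4), and the success criterion uses only the two primary endpoints (SAP 5.6). An effect on the primary safety test is remote.

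**What to change.** 1. In the pre-existing condition rule of Protocol 10.1, delete the second condition, which makes reporting depend on a determined relationship to the procedures or devices. Causality is then recorded as an attribute of the event under 10.4 and no longer decides whether it is entered.
2. In the same sentence, replace the reference to study treatment with the 10.5.1 collection period, from induction of anesthesia through Visit 11.
3. Before the safety analysis, have monitors check source documents for worsened baseline conditions that were not entered, enter them, and submit those within the scope of 11.1 to the CEC. Section 10.5.1 already requires all AEs in source, so the information should be there.

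The cost is a short amendment or site letter, some retrospective AE entry and a limited amount of additional adjudication. No endpoint definition, sample size or analysis method changes.

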10.3 Adverse Event Classification

The Investigator is required to provide:

- Time interval of the event;
- Date of event onset and outcome of the event, or date of death;
- Severity of the event;
- Action taken for the medical management of the event;
- Relationship of the event; and
- Indication of whether the event is serious.

Time Interval of Adverse Event

The time interval of the occurrence of the adverse should be assessed in relationship to timing of the Epicardial Surgical Ablation Procedure or the Endocardial EP Ablation Procedure.

Severity of Adverse Events

The intensity of an AE should be assessed. A change in severity may constitute a new reportable AE. The following guideline should be used to determine the severity of each adverse event:

- **MILD:** Awareness of experience, but easily tolerated. No medical intervention required.

- **MODERATE:** Enough discomfort to interfere with usual activities. Medical intervention required.
- **SEVERE:** Inability to carry out usual activities. Medical intervention (including hospitalization or prolongation of hospitalization) required.

10.4 Relationship of Adverse Events

It is the PIs responsibility to assess the relationship of an AE. Adverse events will be assigned an attribution according to the Investigator's best judgement of primary cause. Events will be categorized by relationship to the investigational devices (ASU2, ASU3, ASB2, EMR2, EML2, MAX5, MCR1, MLP1), or the AtriClip (PRO1 or PRO2), procedure [ablation procedure (epicardial or endocardial) or general cardiac surgical procedure, subsequent intervention], concomitant medications, pre-existing condition, intercurrent condition, intercurrent intervention, or unknown.

Device Related Adverse Event: An adverse event, which in the judgment of the Investigator, results from use of the AtriCure Bipolar System, the AtriClip or the endocardial ablation devices.

Procedure Related Adverse Event: An adverse event which, in the judgment of the Investigator, results as a consequence of the procedure (epicardial surgical procedure or endocardial EP procedure or general cardiac surgical procedure, subsequent intervention) and is not specifically related to the use of the AtriCure Bipolar System.

Concomitant Medication-Related Adverse Event: An adverse event is considered to be concomitant medication related when, in the judgment of the Investigator, it is reasonable to believe that the event is associated with concomitant medications used in conjunction with the investigational device and is not otherwise specific to the investigational device (e.g. bleeding associated with anticoagulation medication).

Pre-Existing Condition-Related Adverse Event: An adverse event is considered to be related to a pre-existing condition when, in the judgment of the Investigator, it is reasonable to believe that the event is associated with the subject's pre-existing condition and is not specific to the investigational device, ablation procedure, or general cardiac surgical procedure. Pre-existing conditions that are aggravated or become more severe during or after the procedure should be evaluated on a case-by-case basis to determine if the event may be more appropriately classified as device-, ablation procedure-, or general cardiac surgical procedure-related.

Intercurrent Condition: It is reasonable to believe that the event is directly associated with an intercurrent condition/co-morbidity.

Intercurrent Intervention: It is reasonable to believe that the event is directly associated with an intercurrent intervention which was performed for reasons other than to address a device or ablation/general cardiac surgical procedure related complication.

Unknown – A clinical event (including abnormal laboratory result) that cannot be determined to be related or unrelated to Investigational devices/procedure/drug given information. Reasonable justification need to be provided.

The following definition should be used in determining the relationship of an adverse event:

- **Related** – A clinical event (including abnormal result) that presents a known or suspected relationship between the following categories and the event.
 - investigational devices (ASU2, ASU3, ASB2, EMR2, EML2, MAX5, MCR1, MLP1), or the AtriClip (PRO1 or PRO2);
 - procedure (ablation procedure, epicardial or endocardial) or general cardiac surgical procedure, or subsequent intervention
 - concomitant medications, pre-existing condition, intercurrent condition, intercurrent intervention, or other.

